# 9.10 Health Economics OR Medical Resource Utilization and Health Economics

Health economics/medical resource utilization and health economics parameters will not be evaluated in this study.

#### 10 STATISTICAL CONSIDERATIONS

There are 2 population groups of interest in this study:

- Overall Population: All participants who were randomized to any treatment arm in the study.
- s-PGA  $\geq$  3 Sub-Population: All participants who were randomized to any treatment arm in the study s-PGA  $\geq$  3 at baseline.

The statistical hypotheses associated with the primary endpoint (DLQI 0/1) and the secondary endpoints (at least a 4-point reduction from baseline in DLQI, whole-body itch NRS score and s-PGA 0/1 [s-PGA  $\geq$  3 Sub-Population only]), will be formally tested in each population group

# 10.1 Statistical Hypotheses

The primary hypotheses for the study are that the odds of achieving DLQI 0/1 at Week 16 in participants receiving deucravacitinib 6 mg QD are improved compared to participants receiving placebo on both the Overall Population and s-PGA  $\geq$  3 Sub-Population.

The null hypotheses to be tested for the primary endpoint are the following:

- The odds of achieving DLQI 0/1 at Week 16 in participants receiving deucravacitinib 6 mg QD are the same as participants receiving placebo on the Overall Population.
- The odds of achieving DLQI 0/1 at Week 16 in participants receiving deucravacitinib 6 mg QD are the same as participants receiving placebo on the s-PGA ≥ 3 Sub-Population.

Key secondary endpoints and associated hypotheses will be tested in a hierarchical order only if both primary hypotheses achieved statistical significance. The null hypotheses corresponding to the key secondary endpoints are described below by population.

[figure not shown]
# Overall Population:

[figure not shown]
- The odds of achieving at least a 4-point reduction from baseline in DLQI at Week 16 in participants receiving deucravacitinib 6 mg QD are the same as participants receiving placebo.
- The mean change from baseline in whole-body itch NRS score at Week 16 in participants receiving deucravacitinib 6 mg QD is not different from participants receiving placebo.

# s-PGA ≥ 3 Sub-Population:

- The odds of achieving at least a 4-point reduction from baseline in DLQI at Week 16 in participants receiving deucravacitinib 6 mg QD are the same as participants receiving placebo.
- The mean change from baseline in whole-body itch NRS score at Week 16 in participants receiving deucravacitinib 6 mg QD is not different from participants receiving placebo.
- The odds of achieving s-PGA 0/1 with at least a 2-point reduction from baseline at Week 16 in participants receiving deucravacitinib 6 mg QD are the same as participants receiving placebo.

# 10.3 Analysis Sets

For purposes of analysis, the populations and analysis data sets are defined in Table 10.3-1.

Table 10.3-1: Populations and Analysis Data Sets

Population	Description
Enrolled	All participants who sign informed consent.
Randomized (FAS)	All participants who were randomized to any treatment arm in the study.
Full Analysis Subgroup	All participants who were randomized to any treatment arm in the study and baseline s-PGA $\geq$ 3.
Safety	All randomized participants who take at least 1 dose of study intervention. Participants will be analyzed according to intervention received.
Defined Analysis Data Sets	Description
Analysis set for primary estimand of DLQI 0/1	All randomized participants with baseline s-PGA $\geq$ 3; all available data up to Week 16 database lock. Participants who discontinue prior to Week 16 will be imputed as non-responders in the analysis dataset. Following the intent-to-treat principle, participants will be analyzed according to the intervention group assigned at randomization.
	All randomized participants; all available data up to Week 16 database lock. Participants who discontinue prior to Week 16 will be imputed as non-responders in the analysis dataset. Following the intent-to-treat principle, participants will be analyzed according to the intervention group assigned at randomization.
	All randomized participants with baseline s-PGA ≥ 3; all available data up to Week 16 database lock. Participants who discontinue prior to Week 16 will be imputed as non-responders in the analysis dataset.

Defined Analysis Data Sets	Description
Analysis set for secondary estimand of ≥ 4-point reduction in DLQI from baseline	Following the intent-to-treat principle, participants will be analyzed according to the intervention group assigned at randomization.
	All randomized participants; all available data up to Week 16 database lock. Participants who discontinue prior to Week 16 will be imputed as non-responders in the analysis dataset. Following the intent-to-treat principle, participants will be analyzed according to the intervention group assigned at randomization.
Analysis set for secondary estimand of whole-body itch NRS	All randomized participants; all available data up to Week 16 database lock. Participants who discontinue prior to Week 16 will be imputed using multiple imputation in the analysis dataset. Following the intent-to-treat principle, participants will be analyzed according to the intervention group assigned at randomization.
	All randomized participants with baseline s-PGA $\geq$ 3; all available data up to Week 16 database lock. Participants who discontinue prior to Week 16 will be imputed using multiple imputation in the analysis dataset. Following the intent-to-treat principle, participants will be analyzed according to the intervention group assigned at randomization.
Analysis set for secondary estimand of s-PGA 0/1	All randomized participants with baseline s-PGA $\geq$ 3; all available data up to Week 16 database lock. Participants who discontinued prior to Week 16 will be imputed as non-responders in the analysis dataset. Following the intent-to-treat principle, participants will be analyzed according to the intervention group assigned at randomization.
Analysis set for safety	All safety events reported for all randomized participants who are exposed to study intervention. For participants who discontinue study intervention all post-discontinuation up to day 28 post last dose of study intervention will be included in the safety summaries.  Participants will be analyzed according to intervention received.

DLQI, Dermatology Life Quality Index; FAS, Full Analysis Set; NRS, Numerical Rating Scale; s-PGA, static Physician Global Assessment.

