		Serum (minimum sensitivity equivalent units 25 IU/L or equivalent units of hCG) to be done at the Screening Visit.
		The participant must be excluded from participation if the serum pregnancy result is positive.
		If needed to document postmenopausal status, as defined in Section 9.4.
FSH	X	Females under the age of 55 years must have a serum FSH level > 40 mIU/mL to confirm menopause.
AE Reporting	-	
Monitor for SAEs	X	All SAEs must be collected from the date of participant's written consent until 30 days post discontinuation of dosing or participant's participation in the study if the last scheduled visit occurs at a later time. All AE (SAEs or nonserious AE) related to SARS-CoV-2 infection collected from time of consent.
AE, adverse event;		BMI, body mass index;
ECG, electrocardiogram;	teractive response technolo	FSH, follicle-stimulating hormone; hCG, human chorionic gonadotropin;
PE, physical examination;		
SAE, serious adverse eve		acute respiratory syndrome coronavirus 2; Organization; WOCBP, women of childbearing potential.

Table 2-2: Day -14 and On-Intervention Procedural Outline (IM011237), Day 1 Through Week 20

Procedure	Week -2 D -14 (±1 d) Visit 1	Day 1 Visit 2	Week 1  D8  (±3 d)  Visit 3	Week 2 D15 (±3 d) Visit 4	Week 4 D29 (±3 d) Visit 5	Week 8 D57 (±3 d) Visit 6	Week 12 D85 (±3 d) Visit 7	Week 16 D113 (±3 d) Visit 8	Week 20 D141 (±3 d) Visit 9	Notes
Eligibility Assessments										
Inclusion/Exclusion Criteria		X								
Medical History		X								
Safety Assessments	•									
Targeted PE		X	X	X	X	X	X	X	X	
Body Weight		X						X		
Vital Signs	X	X	X	X	X	X	X	X	X	
Concomitant Medication Use	X	X	X	X	X	X	X	X	X	
AE Reporting										
Monitor for SAEs	X	X	X	X	X	X	X	X	X	
Monitor for Nonserious AEs		X	X	X	X	X	X	X	X	

Table 2-2: Day -14 and On-Intervention Procedural Outline (IM011237), Day 1 Through Week 20

Procedure	Week -2 D -14 (±1 d)	Day 1 Visit 2	Week 1 D8 (±3 d)	Week 2 D15 (±3 d)	Week 4 D29 (±3 d)	Week 8 D57 (±3 d)	Week 12 D85 (±3 d)	Week 16 D113 (±3 d) Visit 8	Week 20 D141 (±3 d) Visit 9	Notes
Laboratory Tests	Visit 1		Visit 3	Visit 4	Visit 5	Visit 6	Visit 7	V ISIT O	VISIT	
Laboratory Tests										
Pregnancy Test (Urine)		X			X	X	X	X	X	WOCBP only
Efficacy Assessments	1	1					1			
PASI		X	X	X	X	X	X	X	X	
s-PGA		X	X	X	X	X	X	X	X	
ss-PGA		X	X	X	X	X	X	X	X	
PGA-F		X	X	X	X	X	X	X	X	
pp-PGA		X	X	X	X	X	X	X	X	
I-s-PGA		X	X	X	X	X	X	X	X	
s-PGA-G		X	X	X	X	X	X	X	X	
sf-PGA		X	X	X	X	X	X	X	X	

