Safety Assessments					_		
Complete PE					X	X	
Targeted PE	X	X	X	X			
Body Weight					X	X	
Vital Signs	X	X	X	X	X	X	
Concomitant Medication Use	X	X	X	X	X	X	
AE Reporting							
Monitor for AEs and SAEs	X	X	X	X	X	X	
Pregnancy Test (Urine)	X	X	X	X	X	X	WOCBP only
Clinical Efficacy Assessments	V	V	V	V	V		
PASI	X	X	X	X	X		
BSA	X	X	X	X	X		
s-PGA	X	X	X	X	X		
ss-PGA	X	X	X	X	X		
PGA-F	X	X	X	X	X		

Table 2-3: On-Intervention Procedural Outline, (IM011237) Week 24 Through Week 52

Procedures	Week 24 D169 (±3 d) Visit 10	Week 28 D197 (±3 d) Visit 11	Week 32 D225 (±3 d) Visit 12	Week 40 D281 (±3 d) Visit 13	Week 52 (EOT or ET a ) D365 (±3 d) Visit 14	Safety Follow-up (Week 56 or Post-Treatment Follow up a ) D393 (±3 d) Visit 15	Notes
pp-PGA	X	X	X	X	X		
I-s-PGA	X	X	X	X	X		
s-PGA-G	X	X	X	X	X		
sf-PGA	X	X	X	X	X		

Table 2-3: On-Intervention Procedural Outline, (IM011237) Week 24 Through Week 52

Procedures	Week 24 D169 (±3 d) Visit 10	Week 28 D197 (±3 d) Visit 11	Week 32 D225 (±3 d) Visit 12	Week 40 D281 (±3 d) Visit 13	Week 52 (EOT or ET a ) D365 (±3 d) Visit 14	Safety Follow-up (Week 56 or Post-Treatment Follow up a ) D393 (±3 d) Visit 15	Notes
Study Intervention							
Dispense Study Intervention	X	X	X	X			
Study Intervention Compliance	X	X	X	X	X		
Dispense Wristwatch				X			
Collect Wristwatch					X		
Collect e-diary					X		
AE, adverse event; BSA, body surface area; d, da EOT, end of treatment; ET, early termination; I-s- PASI, Psoriasis Area and Severity Index;  Physician Global Assessment;  SAE, serio Face; s-PGA, static Physician Global Assessment;	PGA, Intertrigues	ent;	PE, 1	ohysical exar	sf-PGA, s	igational product; Physician Global Asse pp tatic Physician Globalss-PGA, scalp-specifi	-PGA, palmoplantar

<sup>a EOT/ET visit for participants who discontinue treatment any time prior to completing Week 52 of active treatment period. Safety follow-up visit occurs 28 days ± 3 days after the last dose of study treatment.

Note: When multiple assessments are conducted at a single visit, the following is the order in which they should be done as applicable:

- 1)
- 2) Safety assessments (eg, vitals, AEs)
- 3) Clinical efficacy assessments
- 4) Laboratory tests (eg, safety laboratory tests).

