#### 5.1.5 Week 52 and Safety Follow-up Period

[figure not shown]
The safety follow-up period is a 28-day window after the Week 52 visit. The participant will be encouraged to report any SAEs or AEs experienced during this time.

The end of treatment (EOT) visit will be completed for participants who discontinue study intervention early. The participant will be asked to return to the clinic to complete the 28-day safety follow-up visit.

All participants will return their wristwatches at the Week 52 visit.

The study design schematic is presented in Figure 5.1.5-1.

Figure 5.1.5-1: Study Design Schema

PBO, placebo; QD, once daily.

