## 9.2.2 Time Period and Frequency for Collecting AE and SAE Information

The collection of nonserious AE information should begin at initiation of study intervention until discharge from the study (ie, final study visit for a given participant), at the timepoints specified in the Schedule of Activities (Section 2).

Appendix 1 of the IB represents the Reference Safety Information to determine expectedness of SAEs for expedited reporting.

All SAEs must be collected from the time of signing the consent, including those thought to be associated with protocol-specified procedures, and within 30 days following discontinuation of dosing.

The investigator must report any SAE that occurs after these time periods and that is believed to be related to study intervention or protocol-specified procedure.

- Medical occurrences that begin before the start of study intervention but after obtaining informed consent will be recorded on the appropriate section of the CRF module.
- All SAEs will be recorded and reported to Sponsor or designee within 24 hours, as indicated in APPENDIX 3.
- The investigator will submit any updated SAE data to the Sponsor or designee within 24 hours of updated information being available.

Investigators are not obligated to actively seek AEs or SAEs in former study participants. However, if the investigator learns of any SAE, including a death, at any time after a participant has been discharged from the study, and he/she considers the event reasonably related to the study intervention or study participation, the investigator must promptly notify the Sponsor.

The method of evaluating and assessing causality of AEs and SAEs and the procedures for completing and reporting/transmitting SAE reports are provided in APPENDIX 3.

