#### 10.4.5.1 Adverse Events

Treatment-emergent AEs, SAEs, deaths, AEs leading to study intervention discontinuation, will be summarized by the Medical Dictionary for Regulatory Activities (MedDRA) system organ class and preferred term.

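### Does the day-28 limit on post-discontinuation safety data in Table 10.3-1 wrongly drop events that the protocol collects to day 30 or 31?

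*Combined protocol and SAP*

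**What the plan says.** The safety row of Table 10.3-1 (Section 10.3) has two sentences on scope. The first is general: "All safety events reported for all randomized participants who are exposed to study intervention". The second concerns those who stop: "For participants who discontinue study intervention all post-discontinuation up to day 28 post last dose of study intervention will be included" in the safety summaries. It has no noun after its adjective, and it contains neither an exclusion nor the word only.

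The collection rules are elsewhere:

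- **SAEs, Section 9.2.2:** from consent "and within 30 days following discontinuation of dosing".
- **SAEs, Table 2-1 (Section 2):** "until 30 days post discontinuation of dosing or participant's participation in the study if the last scheduled visit occurs at a later time".
- **Nonserious AEs, Section 9.2.2:** from the start of study intervention to the participant's final study visit.
- **Follow-up visit, Table 2-3 footnote a:** "Safety follow-up visit occurs 28 days ± 3 days after the last dose of study treatment". Section 5.1.5 says of early discontinuers: "The participant will be asked to return to the clinic to complete the 28-day safety follow-up visit".
- **Longer follow-up, Section 8.1.2:** participants who stop study intervention continue to be followed for outcome data until the study concludes.

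On analysis, Section 10.4.5.1 states: "Treatment-emergent AEs, SAEs, deaths, AEs leading to study intervention discontinuation, will be summarized by" MedDRA class and term. The supplied text gives no post-dose window for treatment-emergent. Sections 10.4 and 10.6 leave further analysis detail to a separate SAP, which is not in the supplied file.

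**The concern.** Three numbers describe nearly the same period: 28 days for summarizing, 30 for collecting SAEs, and up to 31 for collecting nonserious AEs if the follow-up visit is at the end of its window. Because the first sentence of the table cell already covers all reported events, the second seems to add something only if it restricts. On that reading, an SAE on day 29 or 30 must be collected from a discontinuer but is missing from the tables.

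The sentence names discontinuers only, so the same event in a Week 52 completer would be counted. Discontinuers include people who stopped because of an adverse event, which makes differential counting unwelcome. No other post-dose analysis window is stated. What would be at stake is under-counting of late events in the group where they might matter most.

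**Working it through.** **The plan's own day count.** Table 2-3 puts Week 52 at D365 and safety follow-up at D393. 365 + 28 = 393, so day 28 is the nominal follow-up day and the analysis limit matches it.

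**Size of the gap in days.**

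- Visit window: 28 - 3 = 25 to 28 + 3 = 31.
- SAEs: 30 - 28 = 2 days, which is 2/30 = 6.7% of the post-dose collection period.
- Nonserious AEs: at most 31 - 28 = 3 days, which is 3/31 = 9.7%. The gap is zero if the visit falls on or before day 28.

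**Expected events in the gap.** The documents give neither a discontinuation rate nor event rates, so these are assumptions: 5-20% of 174 stop early, 5-10 SAEs and 100-300 AEs per 100 participant-years, and Poisson counts. Discontinuers: 0.05 × 174 = 8.7 to 0.20 × 174 = 34.8.

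Expected events = discontinuers × gap days / 365.25 × annual rate. P(at least one) = 1 - exp(-expected).

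| Case | Gap days per discontinuer | Participant-years | Expected events | P(at least one) |
|---|---|---|---|---|
| SAEs, 30-day rule | 2 | 0.048-0.191 | 0.0024-0.019 | 0.2%-1.9% |
| AEs, every visit on day 31 | 3 | 0.071-0.286 | 0.071-0.86 | 7%-58% |
| AEs, visits even over days 25-31 | 0.86 | 0.020-0.082 | 0.020-0.25 | 2%-22% |
| AEs, every visit by day 28 | 0 | 0 | 0 | 0 |

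For evenly spread visits, the mean excess is (0+0+0+0+1+2+3)/7 = 6/7 = 0.86 days. The day-31 row is an upper extreme, since it puts every visit on the last permitted day. Its 0.86 is an expected count, not a maximum: a Poisson variable with that mean is two or more with probability 1 - exp(-0.857) × (1 + 0.857) = 21%.

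Table 2-1 extends SAE collection to a later last visit. If every such visit were on day 31, the SAE gap would be 3 days and the expectation 0.071 × 0.05 = 0.0036 to 0.286 × 0.10 = 0.029.

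**The randomized comparison.** Week 16 is D113. Day 29 after the last dose falls on or before D113 only if the last dose was on or before D113 - 29 = D84. Later discontinuers contribute no gap days to the placebo-controlled period, so the effect there is smaller still.

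**Exposure.** Section 9.3 equates 5 half-lives with about 3 days. Day 28 is 28/3 = 9.3 times that interval, so events on days 29-31 occur long after exposure has ended.

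**Section 8.1.2 beside Table 10.3-1.** If discontinuers really are followed to the end of the study, their final visit, and with it nonserious AE collection, could fall well after day 31. The 3-day figure would then be too small as a count of collected days. But a per-participant limit would then have an obvious purpose: to keep months of off-drug follow-up out of on-treatment safety summaries and to give discontinuers a post-dose window close to that of completers, whose scheduled participation ends about 28 days after Week 52.

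**The case for a change.** The best argument for a change is that the text is unclear and the remedy is cheap. If the day-28 sentence does not limit, it appears to do nothing. If it does limit, discontinuers and completers are treated differently by two or three days with no stated reason. The sentence is also grammatically incomplete, and a programmer working from the protocol alone could not be sure which reading is meant. Aligning the windows would need no new data.

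The day counts and the drafting slip stand. The rest is weaker. The sentence has a second natural use: to make clear that events after stopping still count, rather than to remove them. It says what is included and does not say what is excluded. The reason for 28 can be seen in the visit schedule. The asymmetry with completers exists only on the limiting reading, and Section 8.1.2 gives a reason for a limit that applies to discontinuers. Finally, the post-dose window for treatment-emergent events is a detail normally settled in the SAP, to which the protocol defers. Its absence from the supplied text does not show that it is undefined.

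**Conclusion.** No change to the plan follows. Two windows with different purposes, collection and summary, differ by two or three days, and a summary window shorter than the collection window is not an error. Analysts defining treatment-emergent events will have to choose a post-dose window in any case, and 28 or 30 days are both sensible.

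Under the assumed rates, the expected loss from the summaries on the strictest reading is 0.002-0.02 SAEs (below 0.03 even if every follow-up visit fell on day 31). For nonserious AEs it is 0.02-0.25 with evenly spread visits, zero if visits occur by day 28, and 0.86 in the extreme case. These AE figures assume that participation ends at the 28-day visit; under Section 8.1.2 more late events could be collected, but they would be remote from exposure and properly kept apart. SAEs after day 28 are still collected, reported to the sponsor within 24 hours and followed to resolution or stabilization, so no serious safety information is lost. Efficacy, type I error and power are not affected. Choosing another window would gain nothing that could alter a safety conclusion.

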# 10.4 Statistical Analyses

The statistical analysis plan (SAP) will be developed and finalized before the primary analysis database lock and will describe the selection of participants to be included in the analyses, and procedures for accounting for missing, unused, and spurious data. Below is a summary of planned statistical analyses of the primary and secondary endpoints. A description of the participant population will be included in the clinical study report (CSR), including subgroups of age, gender, race and other study specific populations and demographic characteristics. A description of participant disposition will also be included in the CSR.

#### 10.4.1 General Considerations

Categorical data will be summarized as frequency counts and percentages. Continuous data will be summarized using n, mean, standard deviation, median, minimum, and maximum unless otherwise specified. Efficacy values will be summarized for all visits in which the variable is assessed. Baseline values are defined as the last non-missing value prior to the first dose of study drug unless otherwise indicated.

During the first 16 weeks of treatment, data will be presented for the following interventions:

- Deucravacitinib 6 mg QD
- Placebo

After Week 16, data will be presented for the following interventions:

- Deucravacitinib 6 mg QD
- Placebo- deucravacitinib 6 mg QD (starting at Week 16 through Week 52)

The primary endpoint, DLQI 0/1 response, is defined as a proportion of participants achieving DLQI score of 0 or 1 at Week 16. The key secondary endpoints assessed at Week 16 are  $\geq$  4-point reduction from baseline in DLQI, change from baseline in whole-body itch NRS score and s-PGA 0/1 response. s-PGA 0/1 is defined as a proportion of participants with a s-PGA score of 0 (clear) or 1 (almost clear) with at least a 2-point reduction from baseline at Week 16.

Table 10.4.1-1: Definition of Estimands for Primary and Key Secondary Endpoints

Primary Endpoint			
Estimand Attribute	Definition		
Treatment	Deucravacitinib 6 mg QD v	ersus placebo	
Population	FAS population and FAS su	b-population	
Variable	DLQI 0/1		
ICEs	Event	Strategy	Description
	Discontinuation of intervention or study early prior to Week 16 assessment	Composite variable	Participant will be counted as a non-responder
	Lost to follow-up prior to Week 16 or otherwise missing endpoint data at Week 16 assessment	Composite variable	Participant will be counted as a non-responder
	Start a protocol prohibited medication/therapy	Treatment policy	Participants will be included in the primary analysis regardless of the occurrence of the ICE according to the respective endpoint definition.
	Missing assessment at Week 16 due to SARS-CoV-2	While on treatment	Participants will be excluded from the primary analysis if the Week 16 assessment was not completed due to SARS-CoV-2
Population-level Summary	Odds ratio of achieving DLQI 0/1		

Table 10.4.1-1: Definition of Estimands for Primary and Key Secondary Endpoints

Key Secondary Endpoi	nts			
Estimand Attribute	Definition			
Treatment	Deucravacitinib 6 mg QD versus placebo			
Population	FAS population and FAS su	ıb-population		
Variable	≥ 4-point reduction from ba	seline in DLQI		
ICEs	Event	Strategy	Description	
	Discontinuation of intervention or study early prior to Week 16 assessment	Composite variable	Participant will be counted as a non-responder	
	Lost to follow-up prior to Week 16 or otherwise missing endpoint data at Week 16 assessment	Composite variable	Participant will be counted as a non-responder	
	Start a protocol prohibited medication/therapy	Treatment policy	Participants will be included in the analysis regardless of the occurrence of the ICE according to the respective endpoint definition.	
	Missing assessment at Week 16 due to SARS-CoV-2	While on treatment	Participants will be excluded from the analysis if the Week 16 assessment was not completed due to SARS-CoV-2	
Population-level Summary	Odds ratio of achieving ≥ 4	Odds ratio of achieving ≥ 4-point reduction from baseline in DLQI		
Estimand Attribute	Definition			
Treatment	Deucravacitinib 6 mg QD v	ersus placebo		
Population	FAS population and FAS su	FAS population and FAS sub-population		
Variable	Change from baseline in wh	nole-body itch N	NRS score	
ICEs	Event	Strategy	Description	
	Discontinuation of intervention or study early prior to Week 16 assessment	Composite variable	Missing data will be imputed using multiple imputation	
	Lost to follow-up prior to Week 16 or otherwise missing endpoint data at Week 16 assessment	Composite variable	Missing data will be imputed using multiple imputation	
	Start a protocol prohibited medication/therapy	Treatment policy	Participants will be included in the analysis regardless of the occurrence of the ICE according to the respective endpoint definition.	

**Table 10.4.1-1:** Definition of Estimands for Primary and Key Secondary Endpoints

	Missing assessment at Week 16 due to SARS-CoV-2	While on treatment	Participants will be excluded from the analysis if the Week 16 assessment was not completed due to SARS-CoV-2
Population-level Summary	Adjusted mean difference b	etween deucrav	vacitinib 6 mg QD and placebo
Estimand Attribute	Definition		
Treatment	Deucravacitinib 6 mg QD v	ersus placebo	
Population	FAS sub-population		
Variable	s-PGA 0/1		
ICEs	Event	Strategy	Description
	Discontinuation of intervention or study early prior to Week 16 assessment	Composite variable	Participant will be counted as a non-responder
	Lost to follow-up prior to Week 16 or otherwise missing endpoint data at Week 16 assessment	Composite variable	Participant will be counted as a non-responder
	Start a protocol prohibited medication/therapy	Treatment policy	Participants will be included in the primary analysis regardless of the occurrence of the ICE according to the respective endpoint definition.
	Missing assessment at Week 16 due to SARS-CoV-2	While on treatment	Participants will be excluded from the primary analysis if the Week 16 assessment was not completed due to SARS-CoV-2
Population-level Summary	Odds ratio of achieving s-PGA 0/1		

DLQI, Dermatology Life Quality Index; FAS, Full Analysis Set; ICE, intercurrent event; NRS, Numerical Rating Scale; QD, once daily; SARS-CoV-2, severe acute respiratory syndrome coronavirus 2; s-PGA, static Physician Global Assessment.

